This study will employ an intra-individual balanced 2 x 18-day in-hospital protocol (experimental insomnia vs. control sleep condition, see **Figure 8**). The first 2 nights of each 18-day protocol will be adaptation nights, and the 3rd night will serve as the baseline night, with a sleep opportunity of 8 hours (23pm-7am) on all 3 nights. In the experimental insomnia study arm, insomnia symptoms will be induced during the next 3 nights, followed by 1 night of 8-hour recovery sleep (for more details, see model description under Procedures). During nights with insomnia symptom induction, sleep onset will be delayed by 1 hour (midnight 12am), the sleep period (12-6am) will be disrupted by hourly 20 min long awakenings, and sleep offset will be advanced by 1 hour (6am). This episode of 3 nights of experimental insomnia followed by 1 night of recovery sleep will be repeated three times. After the last experimental insomnia episode, participants will have 4 recovery nights. In the control arm of the study, participants will receive an 8-hour sleep opportunity for all 18 nights of the protocol. These 2 arms of the study will be separated by an interval of at least 1 month in order to allow recovery from blood sampling. Monthly separation was chosen to control for potential effects of menstrual phase in women. Depending on the bed occupancy space, participants will stay in a private room in the CRC. If a private room is not available, participants will stay in a double occupancy room with an individual of the same sex (assigned at birth)

Visit 1. Initial screening. All potential participants will have the study explained to them in detail by the PI or another senior member of the research team. If interested, potential participants will sign the informed consent and nursing staff in the Clinical Research Center (CRC) will take vital signs and collect a blood sample. A short battery of screening tests and questionnaires will also be collected in order to assess health status (see **Appendix 1** for blood tests and questionnaires). Potential participants will then be introduced to the web-based, secured diary recording system (REDCap²²) and given an actigraphy watch to take home to estimate sleep-wake habits, for 2 weeks (see **Appendix 1**). These data will be used to verify nightly sleep duration between 7 to 9 hours to be used for eligibility.

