The Cold Pressor Test (CPT): This test requires the insertion of the hand into an ice-cold water bath (Techne® water baths, Bibby Scientific US, Burlington, NJ) held at a temperature of 3°C. Participants are instructed to leave their hand in the water bath for at least 1 minute and are told that they may remove their hand earlier if the pain gets unbearable. Maximum immersion time will be 3 minutes. Pain intensity and unpleasantness will be rated every 10 sec during the hand immersion, as well as every 10 sec for 2 minutes and 30 seconds post-testing to capture recovery slopes.

Statistical Considerations

Sample size: 34 subjects (including a 32% discontinuation rate) will run in balanced order through the two protocols, each consisting of a 18-day in-hospital stay (separated by an interval of 1 month or more) in order to complete the study with 26 subjects. **Power calculations** for the inflammatory response (aim 1) were estimated using findings coming from sleep restriction models on IL-6 (plasma levels and expression by monocytes). For the pain-inhibitory response (aim 2), we estimated power using the effects of a single episode of sleep disruption on the pain-inhibitory capacity³⁷. For the recovery response (aim 3), we used data from the effects of recovery sleep on IL-6 positive monocytes, as well as on the habituation to pain in the cold pressor test paradigm (data obtained in currently ongoing protocol). For all 3 aims, optimal power will be reached with a sample size of N=26 (see **Table 1**).

Randomization: Block randomization will be used with block sizes of 10, 8, 8, and 8. Each block will have equal numbers of females and males and equal numbers of sequences (1. insomnia induction – control sleep, 2. control sleep – insomnia induction). Randomization will be prepared by the study statistician and the participant will be informed of the sequence on study day 1.

Statistical Analysis:

Table 2 shows the primary outcome variables for aim 1-3, as well as secondary outcome variables used for explorative analysis (not part of aims).

Some of the variables will be measured at different time scales and reduced to the following summary variables: Subjective estimations of emotional and physical well-being assessed every 4 hours during the waking periods (and after each nighttime awakening during insomnia induction nights) of the protocol will be averaged to nighttime and daytime frequency and intensity measures.

Table 2: Outcome variables			

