Outcome variables will be measured on 8 out of the 18 in-hospital protocols (baseline, 2nd experimental insomnia/control night and 4th recovery night of each episode, and 3rd recovery night at end of protocol). The analysis will focus on episode-wise comparison of outcome variables between experimental insomnia and control sleep conditions. Although several forms of linear mixed model will be used, our main analysis will focus on daily summary measures (mean, max, min, slope, AUC, etc.) The models will be constructed as follows: the study has two within factors (measurements over several days and measurements within the same day). Data will be used as it is or the difference between the two experimental conditions by episode will be used in the analysis. The main method of data analysis will employ linear mixed model (repeated measures analysis).

By defining appropriate contrast we can evaluate (i) the difference between experimental insomnia nights and recovery sleep nights for the entire study period, (ii) the difference between days 3 and 6 (day6 minus day3), 7 and 10, and 11 and 14 separately. We expect that each of the contrasts will yield a significantly positive value. These comparisons will show if IL-6 values drops or increases from experimental insomnia nights to recovery sleep nights. Similarly, from the same model, by defining appropriate contrasts, we will evaluate the difference between days 6 and 7, 10 and 11, and 14. These contrasts are expected to be negative. Time will also be used as a continuous variable to test the trend and quadratic effect, and if the above contrast does not suggest strong episode-wise effect but mild increment (or decrease) from one episode to the next. We may also use piece-wise regression with a knot at each episode (and also with just one knot to capture the effect of prolonged recovery towards the end of the experiment). As mentioned earlier, many of the exploratory analysis will be guided by plots and summary assessment of the data. Other inflammatory marker (PEG2, resolvins) will be analyzed in a similar fashion.

Sensitization variables (HPT, PPT, TS) will be analyzed similarly and are expected to mimic the time course of inflammatory variables. Correlation between inflammatory markers and sensitization variables will be evaluating using the Altman-Bland method². The linear mixed model described above can be used to obtain the necessary estimates to compute this correlation.

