Assessment of Aim 2: Pain-inhibitory response and its relation to indicators of habituation to pain upon repeated episodes of experimentally-induced insomnia symptoms. Analysis will follow the strategy similar to one outlined in Aim 1. To evaluate co-variation of the pain-inhibitory response with indicators of habituation we will first obtain average values of each value for each day, and use the Altman-Bland correlation approach described earlier.

These data will be analyzed using linear mixed model for doubly repeated measures using SAS GLM procedure as described in:

http://support.sas.com/documentation/cdl/en/statug/63033/HTML/default/viewer.htm#statug_glm_sect054.htm.

Assessment of Aim 3: Recovery of the inflammatory and pain-inhibitory response upon

repeated episodes of experimentally-induced insomnia symptoms. The proposed incomplete resolution of inflammatory and pain-inhibitory responses during the recovery nights and the progressive impairment of these responses across insomnia induction episodes will be evaluated using a mixed model approach and utilizing four time points: baseline, and recovery at the end of 1st, 2nd, and 3rd insomnia episode. Recovery response will be further evaluated by comparing effects of a single night of recovery sleep to a set of 3 nights of recovery sleep at the end of the protocol. Data analysis for this aim is similar to data analysis described for Aim 1, but a different set of contrasts need to be defined. Our conjecture is that during the recovery IL-6 drops but does not reach to the level of previous recovery. To test this we will evaluate contrasts that compare IL-6 values at days 3 and 7, 7 and 11 and 11 and 15. Finally, the difference between day 15 and 17 is assumed to be larger than any other difference between sleep restriction and recovery days. To test this we will evaluate the differences between other recovery days (average of days 7, 11, and 15) and day 17. All analysis will be performed using SAS statistical package (version 9.3).

C. Subject Selection

Human Subjects Involvement and Characteristics

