A total of 34 healthy adults (18-35 yrs, 17 women, including a discontinuation rate of 32%) will be enrolled. Subjects of all racial/ethnic backgrounds will be eligible to participate (see Planned Enrollment Report for expected distributions). Participants will be accepted into the study if they are in good health, do not have an active medical disorder or history of any medical disorders (including sleep disorders), as determined by a medical history, physical screening, and overnight sleep study (PSG, as per methods). Participants from the Boston area, who meet these strict medical eligibility criteria, will be recruited to participate in the 2 x 18-day in-hospital study. Once participants enter the study, they will stay in a patient room at the Clinical Research Center of Beth Israel Deaconess Medical Center. Nurses will check vital signs daily and will assess general emotional and physical well-being at regular intervals throughout each study day. The study physician will also perform an in-person visit with each participant every day, in order to ensure participant's well-being.

Inclusion Criteria:

- Women and men between the ages 18-35 years.
- Non smoking
- Body mass index (BMI) between 18.5 and 30 kg/m².
- For female participants: regular menstrual cycles, no significant discomfort during pre-menses/menses.
- Daily sleep duration between 7-9 hours, verified by REDCap electronic sleep diary.
- Sleep onset within one hour of 11pm (to ensure normal entrainment).
- Blood chemistry in the normal range.
- Medical examination finding within normal range.

Exclusion Criteria:

- Active infection/disease.
- History of neurological, chronic pain, immune, cardiovascular, liver/kidney, or metabolic disorder or Raynaud's syndrome within 6 months prior to study start.
- Active or chronic psychiatric disorders within 6 months prior to study start, including major depressive disorders, bipolar disorders, panic disorders, post-traumatic stress disorders (PTSD), thought disorders, and substance abuse/dependence disorders.
- In psychotherapy or any other behavioral interventions at study start (eg acupuncture for insomnia)

- Sleep disorders.

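### Sex is balanced in the randomisation but not named in the Aim 1–3 models, so any sex difference in insomnia response stays in the error of the within-person contrasts

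*Combined protocol and SAP*

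**What the plan says.** The design is a two-condition crossover: "This study will employ an intra-individual balanced 2 x 18-day in-hospital protocol". Under Randomization, "Block randomization will be used with block sizes of 10, 8, 8, and 8", and "Each block will have equal numbers of females and males and equal numbers of sequences". Section C, Subject Selection, plans the same split: "A total of 34 healthy adults (18-35 yrs, 17 women, including a discontinuation rate of 32%) will be enrolled". The Study Design section also spaces the two stays so that menstrual phase can be matched.

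The analysis text does not take sex up. Under Assessment of Aim 1, "the study has two within factors (measurements over several days and measurements within the same day"; no between-person factor is listed. The unit of analysis is left open: "Data will be used as it is or the difference between the two experimental conditions by episode will be used in the analysis". For Aim 2, "Analysis will follow the strategy similar to one outlined in Aim 1". For Aim 3, "Data analysis for this aim is similar to data analysis described for Aim 1, but a different set of contrasts need to be defined". In none of the three is sex a factor, covariate, interaction or subgroup.

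**The concern.** A factor held in balance by design would normally appear in the analysis, because balance alone does not remove the variation that the factor causes. In a crossover the relevant variation is narrow. Women and men may differ in their general level of IL-6 or pain threshold without any effect on the within-person comparison. If they differ in how much they respond to the induced insomnia, each person's condition difference varies around the mean of their own sex, and a model without sex counts the gap between the two means as noise.

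What is at stake is some precision on outcomes whose planned power is close to 0.80, and a stated way of averaging over the sexes if completion turns out unequal.

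**Working it through.** **Inputs.** From Table 1: paired t-test, alpha 0.05, N = 26, and the mean and SD of the response difference in each row. Sidedness is not stated; two-sided is assumed. The sex difference in response, D, is not in the documents. I take D = 0.25, 0.5, 0.8 and 1.0, in units of the within-sex SD of the paired difference, and 13 women and 13 men among 26 completers.

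**Step 1: reproduce the plan's figures.** Power comes from the noncentral t with 25 df and noncentrality (mean/SD)·√26. For IL-6 positive monocytes, 38/66 = 0.576 and 0.576 × 5.099 = 2.94.

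| Table 1 row | mean/SD | power |
|---|---|---|
| Plasma IL-6 | 1.95/1.59 = 1.226 | >0.999 |
| IL-6 positive monocytes | 38/66 = 0.576 | 0.806 |
| Pain inhibition (CPM) | 47/54 = 0.870 | 0.989 |
| Cold pressor habituation | 15/25 = 0.600 | 0.836 |
| Cold pressor after recovery | 24/28 = 0.857 | 0.987 |

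All exceed 0.80, as the plan states.

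**Step 2: variance left in the error.** With equal numbers, each sex mean lies D/2 from the overall mean. The total variance of the paired difference is therefore the within-sex variance times 1 + D²/4, which is 1.016, 1.0625, 1.16 and 1.25 for the four values of D.

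**Step 3: power with sex in the model, if Table 1's SD already contains D.** The within-sex SD is 66/√(1 + D²/4), and one df is spent (24 df).

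| D | within-sex SD | monocyte power |
|---|---|---|
| 0 | 66.0 | 0.804 |
| 0.25 | 65.5 | 0.810 |
| 0.5 | 64.0 | 0.827 |
| 0.8 | 61.3 | 0.858 |
| 1.0 | 59.0 | 0.883 |

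The cold pressor habituation row moves in the same way, from 0.836 to 0.841, 0.857, 0.885 and 0.907. The CPM row goes from 0.989 to at most 0.997. Plasma IL-6 has nothing to gain.

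**Step 4: which term does the work.** The Aim 1 and Aim 3 contrasts compare days, for example day 6 minus day 3. Day 3 is baseline in both stays, so the insomnia response is a condition-by-day effect. Sex and sex-by-condition terms are constant over the days of a stay and subtract out of any day contrast. Take the contrast (insomnia day 6 − insomnia day 3) − (control day 6 − control day 3) with independent residuals of variance 1. Its variance is 4. A sex difference in response of one residual SD adds 1²/4 = 0.25, giving 4.25. Sex and sex-by-condition leave 4.25 unchanged; regressing each person's contrast on sex returns it to 4.00. A simulation with a 1-SD sex difference agrees: 4.24 falling to 3.99. One residual SD is half the contrast's own SD of 2, so this is the D = 0.5 line above (4.25/4 = 1.0625).

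**Step 5: what can be said about each sex.** A two-sample t-test on the within-person differences, 13 against 13, has power 0.09, 0.23, 0.50 and 0.69 to detect D = 0.25, 0.5, 0.8 and 1.0. Power of 80% needs D of about 1.15.

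**The case against.** The case for leaving the plan alone has real weight.

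- **The size is hypothetical.** No outcome has a documented sex difference in response, no aim concerns sex, and at D = 0.25 the gain is 0.004. This stands, and the figures are conditional for that reason.
- **The obvious remedy fails.** Adding only sex and sex-by-condition does nothing for the plan's day contrasts (Step 4). This stands, and it determines the form of the fix.
- **A full interaction model is not cheap.** With 8 days and 2 conditions, separate sex effects in every cell need up to 8 × 2 = 16 further parameters for about 26 people. True of that model, but a covariate on each within-person contrast costs one df per contrast.
- **Few outcomes benefit.** Three of the five Table 1 rows are already at 0.987 or above, and the cold pressor test is not a Table 2 primary outcome. This stands.
- **Sex is unnamed, not excluded.** The Aim 1 text allows several forms of mixed model. True, but naming the term in advance avoids a choice made after seeing the data.

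Three stronger readings are tempting, and the documents support none of them. A reader might infer that the insomnia effect is biased; with balanced sexes it is not. Even 15 women and 11 men completing, with D = 0.8, would move the unadjusted mean from the equal-sex average by only (15/26 − 1/2) × 0.8 = 0.06 SD, and nothing in the plan predicts such an imbalance. A reader might infer that power falls below the stated level. If 66 were a within-sex SD, omitting sex would lower monocyte power to 0.782, 0.745 or 0.714 for D = 0.5, 0.8 or 1.0. The documents do not give the sex mix behind Table 1, and if those samples were mixed the stated power already carries this variance. Finally, a reader might say that the analysis breaks with the randomisation. What is randomised is sequence; balancing blocks on sex does not oblige the analyst to model a different response by sex.

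**Conclusion.** The point holds as a minor one. The design balances sex, the analysis does not name it, and any sex difference in response stays in the error of each within-person contrast. On the assumption that Table 1's SD already contains the difference, the power forgone in the monocyte row is about 0.004 to 0.08 for D between 0.25 and 1.0; if there is no difference, adding sex costs about 0.001. The result also assumes two-sided testing, 26 completers split evenly by sex, and a single summary difference per person, as in Table 1. For outcomes planned near 0.99 the choice hardly matters. The condition effect itself is not in doubt.

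**What to change.** State in the Statistical Analysis section that, for each within-person condition difference or day/episode contrast tested under Aims 1–3, sex enters as a between-person covariate coded +1/2 and −1/2. The intercept is then the insomnia effect averaged with equal weight over women and men, whatever the mix of completers. If the full mixed model is used instead, carry sex into the condition-by-day (or condition-by-episode) terms.

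Report the equal-weight effect as the result. Give sex-specific estimates with confidence intervals, labelled descriptive.

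The cost is a sentence or two in the plan and one degree of freedom per contrast, or more parameters if the full sex-by-condition-by-day model is chosen. The sex-specific estimates will be imprecise at about 13 against 13 and should not be read as tests.

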Polysomnographic recording (PSG). Sleep will be recorded using the Embla system N7000 (Medcare US, Buffalo) on the screening night visit to ensure that participants are free from sleep disorders. The Embla system will also be used to collect sleep data on the 8 intensive recording days of each study run (baseline, every 2nd and 4th night of each episode, 3rd recovery night at end of protocol). The PSG montage will follow standard criteria and sleep EEG will be manually stage-scored on a 30 second epoch basis³. The main purpose for sleep data collection is the quantification and comparison of various sleep indices in insomnia symptoms induction and control nights (e.g., sleep duration, sleep latencies, percent time spend in different sleep stages). For explorative analysis (not specified in aims), spectral analyses will be conducted on EEG data using Remlogic software (Medcare US, Buffalo). The homeostatic response will be calculated for each episode, by calculating change from baseline for the two homeostatic markers N3 (slow wave sleep) and delta power, and comparing between episodes. We will explore whether the robust and stable homeostatic response that has been observed within exposure to a single episode of deficient sleep¹ will increase with episode repetition. Spectral analysis will be performed by the PI, who is experienced in this analysis¹⁹.

Blood Sampling. On the baseline day (Day 3), as well as on the 8 intensive recording days of each 18-day study run, blood samples will be drawn at 1100am and after pain testing, around 1550 (50 min after pain testing) per simple needle stick. The amount of the blood collected at each blood draw will range between 10ml and 50ml. The total amount of blood taken over each 18-day protocol will not exceed 550ml.

IL-6 will be measured in plasma in our laboratory, using a high sensitivity enzyme immunosorbent assay (ELISA, Quantikine ® HS, R&D Systems, Minneapolis, MN). We will measure IL-6 twice throughout the 8 intensive recording periods. IL-6 will be also measured in vitro as the capacity of monocytes to express IL-6. In brief, whole blood will be stimulated with lipopolysaccharide (LPS,

100pg/ml), incubated with fluorescence-conjugated antibodies (CD14, CD45, IL-6), and IL6-positive monocytes will be quantified using flow cytometry (Gallios™ Beckmann-Coulter Inc, Flow Cytometry Core at BIDMC).

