Assessment of emotional and physical well-being. Every 4 hours during daytime wake periods, as well as after each nighttime awakening during the experimental insomnia induction nights, participants will rate intensity of mood and spontaneous pain symptoms using computerized visual analogue scales (AsWin, programmed by Martin Rivers & Associates, see **Appendix 2**). The test battery requires approximately 5 minutes per administration. Though *spontaneous* pain is not the focus of this grant, we will explore whether processes of inflammatory-induced sensitization and pain-inhibitory induced habituation to evoked pain may relate to the experience of spontaneous pain.

Pain testing battery: Pain sensitivity and pain inhibition tests will be administered at 2pm throughout the 8 intensive recording days. Throughout the 1 hour testing period, the participant will remain in a seated position in a comfortable chair. The sequence of laboratory events is as following (see **Appendix 3** for a detailed description of tests, as well as²¹).

- (1) Pain sensitivity tests: (a) Heat pain thresholds (HPT), (b) Pressure pain thresholds (PPT)
- (2) Pain modulation tests: (a) Temporal summation of heat pain (TS). (b) Conditioned pain modulation (CPM)
- (3) Cold pressor test (CPT)

We plan to apply heat stimuli using the Pathway Model CHEPS (Medoc, Minneapolis, MS), which has the advantage of a rapid and flexible heating rate required for TS testing (see Budget Justification). Pressure stimuli will be applied using an electronic pressure algometer (Somedic Sales AB, Hörby, Sweden). For heat pain applications at the foot (being applied in TS), we will use a temperature-controlled water bath (Techne® water baths, Bibby Scientific US, Burlington, NJ). The proposed

inflammatory-induced sensitization should manifest in lower HPT and PPT, as well as increased TS of pain (used as an index of central sensitization). The proposed failure of the pain inhibition system (measured through CPM), should result in a lack of habituation to pain, as measured by heat pain supra-thresholds throughout the 8 intensive recording days of the experimental insomnia induction or control sleep protocol.

Pain testing details:

(1) Pain sensitivity tests:

[figure not shown]

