- (a) Heat pain thresholds (HPT, 10min) will be assessed using a precise, computer-controlled thermode (Somatosensory Analyzer, Medoc, Minneapolis, MS) for generating and recording responses to thermal stimuli. The thermode will be attached to the forearm volar skin of the arm not used for blood draws, via a Velcro strap, to the palm. From a baseline temperature of 32°C, the thermode is heated at a rate of 0.5 °C/sec. The participant is instructed to click a computer mouse with their free hand, as soon as heat pain is perceived. To improve accuracy, each threshold will be measured 4 times. The inter-stimulus interval is 15 sec, and the average will be used for further analysis.
- (b) Pressure pain thresholds (PPT, 10min) will be obtained with use of an electronic pressure algometer (Somedic Sales AB, Hörby, Sweden), and assessed at the posterior neck, trapezius muscle, and middle phalanx of the middle/ring finger, and pressure will be increased at a rate of 30 kPa/s. Participants will be instructed to press a control button when they experienced the first sensation of pain. A series of four pressure-pain stimuli will be applied with 15 sec intervals to each side, and the average of these stimuli will be calculated.

(2) Pain modulation tests:

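### Participants are told their sequence on study day 1, two days before the day-3 baseline pain tests, although the conditions do not differ until night 4 and no reason is given

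*Combined protocol and SAP*

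**What the plan says.** Under Statistical Considerations, Randomization, blocks contain "equal numbers of sequences (1. insomnia induction – control sleep, 2. control sleep – insomnia induction"), and "the participant will be informed of the sequence on study day 1". With only two sequences, learning the order reveals the condition of both stays. I read study day 1 as day 1 of the first stay.

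The Study Design section sets the calendar: "The first 2 nights of each 18-day protocol will be adaptation nights, and the 3rd night will serve as the baseline night", all three with the same 8-hour sleep opportunity. In the insomnia arm, "insomnia symptoms will be induced during the next 3 nights, followed by 1 night of 8-hour recovery sleep". The Blood Sampling paragraph confirms the baseline label: samples are taken "On the baseline day (Day 3), as well as on the 8 intensive recording days of each 18-day study run".

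For pain, "Pain sensitivity and pain inhibition tests will be administered at 2pm throughout the 8 intensive recording days", and the description of Visits 3 and 4 counts baseline among those days. The outcomes are participant responses. For heat pain threshold, "The participant is instructed to click a computer mouse with their free hand, as soon as heat pain is perceived"; pressure pain threshold is a button press; temporal summation (TS) and conditioned pain modulation (CPM) are built from visual analogue ratings.

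Assessment of Aim 1 includes "the difference between days 3 and 6 (day6 minus day3"). The Aim 1 contrasts are spelled out for IL-6, and the sensitization variables are to be analysed in the same way. Assessment of Aim 3 adds its own contrasts and a model on four time points, one of them baseline.

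For last-minute cancellations, the Study Design section lets new participants use adaptation day 1 for both the initial and the medical/overnight screening, and go on to adaptation day 2 if they qualify.

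**The concern.** A baseline is normally taken before the allocation is revealed, so that it cannot depend on what the participant expects next. Here it is taken afterwards. A participant who knows that three disrupted nights are about to start may click earlier or later, or rate differently, from one who knows that ordinary sleep will continue.

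The main hypothesis is a progressive change across episodes. Episode 1 is judged against day 3, whereas later episodes are judged against recovery days. A shift on day 3 would therefore alter the apparent size of episode 1 and leave the later within-episode contrasts untouched, which is the pattern that could be mistaken for progression or could hide it. The analysis section uses the data as measured or as between-condition differences and specifies no baseline adjustment.

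There is also a procedural gap. A replacement participant's first study day is also the screening day, so the sequence could be disclosed before eligibility is decided.

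**Working it through.** The plan states no figure on this point, so the check concerns timing, the use of day 3, and what a shift would do.

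**Timing.** Disclosure is on day 1 and baseline on day 3: 3 − 1 = 2 days. Nights 1 to 3 are the same in both conditions, and night 4 is the first that differs. Disclosure after the day-3 tests would still precede the first night on which the participant needs to know.

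**Where day 3 is used.** Day-specific contrasts as listed under Aims 1 and 3:

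| Aim | Contrast | Uses day 3 |
|---|---|---|
| 1 | 6 − 3 | yes |
| 1 | 10 − 7 | no |
| 1 | 14 − 11 | no |
| 1 | 6 v 7 | no |
| 1 | 10 v 11 | no |
| 1 | 14 v (partner not printed; read as 15) | no |
| 3 | 3 v 7 | yes |
| 3 | 7 v 11 | no |
| 3 | 11 v 15 | no |
| 3 | 15 v 17 | no |
| 3 | mean of 7, 11, 15 v 17 | no |

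That is 2 of 11. The overall Aim 1 contrast of insomnia nights with recovery nights does not use day 3 either. The Aim 3 four-time-point model does. The Aim 1 time-trend and piecewise models would use it if they include every measured day, which the plan does not state.

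**Which outcomes are exposed.**
- Heat and pressure pain thresholds are direct responses, so any shift passes straight through.
- TS is the last rating minus the first in a sequence. If every rating in the session moves by s, TS becomes (last + s) − (first + s) = last − first, so s drops out.
- CPM contrasts ratings with and without the hot-water bath, so a uniform s drops out there too. An uneven shift would remain in both.
- IL-6, PGE2 and resolvins are laboratory assays, to which self-report bias does not apply directly.

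**What a shift does.** Let b3, b6, b7 and b10 be the expectation shifts on those days of the insomnia stay.

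- Bias in day 6 minus day 3 = b6 − b3.
- Bias in day 10 minus day 7 = b10 − b7, with no b3 term.
- Bias in the episode 2 contrast minus the episode 1 contrast = (b10 − b7) − (b6 − b3), which contains +b3.

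Hence b3 alone moves the comparison of episode 1 with episode 2. Illustrative values in arbitrary units (assumptions, not from the documents):

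| b3 | b6 | bias in 6 − 3 |
|---|---|---|
| 0 | 5 | 5 |
| 5 | 5 | 0 |
| 2.5 | 5 | 2.5 |
| 5 | 2.5 | −2.5 |

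The sign depends on how b3 compares with b6, and the documents fix neither.

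**How much can be protected.** Each participant has two baselines, one per stay. The second is taken with the condition known by elimination, so later disclosure can protect at most 1 of 2.

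**The case against.** The strongest reply is cancellation. Participants know their condition from night 4 whatever is done. If that knowledge shifts responses equally on days 3 and 6, early disclosure lets the shift cancel (second row of the illustration). Late disclosure would then set a neutral baseline against a shifted day 6 (first row). This stands as a limit: later disclosure cannot be said to reduce the bias in day 6 minus day 3 in every case. It does not defeat the change, because anticipation before any sleep loss need not equal expectation after disrupted nights, and a baseline that does not depend on the allocation is the usual standard.

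Several stronger readings are tempting and are not supported:

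- A reader might infer that every contrast rests on day 3. Only two of the listed contrasts do.
- A reader might infer that day-1 disclosure has no benefit to the trial. The documents give no reason, but silence does not show that there is none.
- A reader might assume a shift in SD units and divide it by the smallest standardised effect in Table 1, 38/66 = 0.576. That effect is for IL-6-positive monocytes, a laboratory measure, and the assumed shift would have no source in the documents.
- A reader might infer that early disclosure drives withdrawal by sequence. Everyone is scheduled for both conditions, and later disclosure would move such withdrawal to after day 3 rather than prevent it.
- A reader might want the pain testers masked until day 3 as well. Research staff accompany participants throughout, and no separate testing team is described, so this would not be a simple wording change.

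**Conclusion.** The concern holds in a limited form. The first-stay baseline of the self-reported pain outcomes, chiefly the heat and pressure thresholds, is measured with the allocation known, and the plan gives no reason. What is at risk is the reading of episode 1 against later episodes, through the day 6 minus day 3 contrast, the day 3 against day 7 contrast and the Aim 3 four-time-point model. No magnitude or direction can be derived from the documents.

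The conclusion assumes that study day 1 means day 1 of the first stay, and that the contrasts written for IL-6 carry over to the pain measures, as the analysis section indicates. The gap for replacements is a possibility left open by the text: the plan does not say whether disclosure waits for eligibility. Overall this is a low-priority improvement that is worth making because it is so cheap.

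**What to change.** Amend the last sentence of the Randomization paragraph so that the participant is told the sequence only after all day-3 baseline assessments of the first stay are complete, and before night 4. This also closes the gap for last-minute replacements, whose screening would by then be finished. If disclosure on day 1 is needed for a practical reason, state the reason instead, and say that replacements are told only once eligibility is confirmed.

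The cost is one sentence and slightly later notice for participants. The change leaves the second-stay baseline and all ratings from night 4 onward unmasked, and the plan should acknowledge this when the pain outcomes are interpreted.
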